1.1 Background

THA is one of the most clinically successful and cost-effective interventions in health care. Numerous surgeons have reported excellent long-term results in terms of reducing pain, improving function and QOL in patients with debilitating hip disease.¹

Cemented as well as cementless hip stems have shown good results in THA, even in younger patients.² Implant design may contribute to the success of an implant. In a multi-center study of 251 cases receiving proximally hydroxyapatite-coated straight, collarless femoral stems manufactured from titanium alloy (OmniFit HA), radiographic evaluations performed by D'Antonio et al.³ indicated a high rate of early and continuing fixation and consistent adaptive bone remodeling around the stem through 6 years postoperative. Fifteen-year results from the same study demonstrated excellent long-term survivorship with a revision rate of 0.6% for both aseptic loosening and mechanical failure of the femoral stem.⁴ Additionally, in a series of 31 bilateral patients implanted with OmniFit HA, Schwarzkopf et al.⁵ observed femoral component survivorship of 100% through the 23-year follow-up period for the 27 patients available.

Following the design philosophy of the successful OmniFit HA stem, the next generation of double-wedge, metaphyseal filling stems introduced by Stryker was the Secur-Fit family. The main design change from OmniFit to Secur-Fit was the addition of a proximal roughened titanium surface to which the hydroxyapatite (HA) is applied. The neck angle of the Secur-Fit stem is 132°; this angle is decreased to 127° in the Secur-Fit Plus design to produce increased femoral offset. In a retrospective review of 105 cases implanted with either Secur-Fit or Secur-Fit Plus at 5 to 10 years postoperative, Incavo et al.⁶ reported that all stems achieved and maintained stable fixation. Equal leg lengths were achieved in 82% of Secur-Fit cases and 92% of Secur-Fit Plus cases, leading the authors to note that availability of both a standard- and high-offset option may facilitate soft-tissue balancing intraoperatively without adversely affecting postoperative leg length.

The stem body design of the Secur-Fit Advanced Hip Stem is based on the Secur-Fit HA Hip Stem (K982032, K041170). Like the predicate for body design, the Secur-Fit Advanced Hip Stem is a straight stem with a normalization pattern on the anterior and posterior aspects of the proximal end to facilitate press-fit stability and load transmission to the proximal region of the femur. Based on 3-Dimensional simulations, these normalizations are designed to convert medial and lateral shear stresses to compressive forces, which may facilitate proximal loading.(RD-13-001). The distal portion of the stem has a polished tip, and the neck region has been polished and shot peened. The stem neck is designed with a Howmedica Osteonics V40 taper on the proximal end and is available in both 127° and 132° neck-stem angles. The Secur-Fit Advanced Hip Stem is manufactured from Titanium (Ti-6Al-4V) alloy with a commercially pure Titanium (CP Ti) and HA coating to establish good initial fixation.

1.2 Study Device

The Secur-Fit Advanced Hip Stem was cleared for use under FDA 510(k) K122853 on February 1, 2013. See Appendix A for the FDA clearance letter.

The Secur-Fit Advanced Hip Stem is intended for cementless, press-fit application, and will be available in nine sizes ranging from size 4 through 12. Sizes 4 and 5 are available with a 132° offset angle only; all other sizes are available in both 127° and 132° offset angles. Details of the device design are presented in Section 6, Device Description.

1.3 Preclinical Data

The following bench tests (with test report numbers) were conducted with the Secur-Fit Advanced Hip Stem:

Coating Thickness (MT01016)

The mean coating thickness for the titanium plasma sprayed coating and Pure-Fix HA coating was 0.446 mm and 0.058 mm respectively.

Tensile Bond Strength (MT01016)

The average tensile strength of the titanium plasma sprayed and Pure-Fix HA coated specimens were 39.11 MPa.

Version 3.0

Shear Bond Strength (MT01016)

The average shear bond strength of the PureFix HA on the titanium plasma sprayed coating was

23.85 MPa.

Fatigue Strength (MT01016)

Fatigue strength of the Titanium Plasma sprayed and PureFix HA coating on the shot peened

Ti6Al-4V ELI substrate was 552 MPa at ten (10) million cycles.

Abrasion Resistance (MT01016)

The average weight loss as a result of abrasion testing of the PureFix HA and Titanium plasma

sprayed coupons was 1.57 mg.

Neck Fatigue Testing (RD-12-092)

All eight 127° Size 8 Secur-Fit Advanced Hip Stems successfully withstood 5340N (1200lbf) for

ten million (10 x 106) cycles without failure and with no loss of mechanical integrity as specified

by ISO 7206-6. Based on loading characteristics, the maximum head offset for the Size 4 stem

is +5 mm.

Distal Fatigue Testing (RD-12-093)

Eight 127° Size 6 representative stems, which were plasma spray HA coated over plasma spray

CP Ti proximal coating, were used for testing. The stems were oriented at 10° valgus/9° flexion

at a potting level of 80 mm from the worst case (+12 mm) head center consistent with ISO 7206-

4. All eight 127° Size 6 Secur-Fit Advanced Hip Stems successfully withstood 2300 N (517 lbf)

for five million (5.0 x 106) cycles without failure and with no loss of mechanical integrity as specified

by ISO 7206-4:2010.

The results of the bench top testing conducted for the new Secur-Fit Advanced Hip Stem identified

acceptance criteria were met.

Copies of all test reports are available at Stryker Orthopaedics.

1.4 Clinical Data to Date

This study is the first Stryker sponsored multi-center prospective data collection on the Secur-Fit

Advanced Hip Stem.

CONFIDENTIAL

2 Study Objectives

2.1 Efficacy

2.1.1 Primary

The primary objective of this study is to evaluate the success rate of cementless primary total hip replacement with the Secur-Fit Advanced Hip Stem. Success will be defined as absence of femoral stem revision for aseptic loosening or device-related femoral fracture at 5 years postoperative. It is expected that the success rate of the Secur-Fit Advanced Hip Stem group will be non-inferior to the selected reference rate of 99% at 5 years postoperative.

2.1.2 Secondary

The secondary objectives of this study will include evaluation of all-cause revision and removal rates with the Secur-Fit Advanced Hip Stem and comparison with those reported for other primary hip systems in the literature.

Additionally, the rate of device-related femoral fracture among patients implanted with the Secur-Fit Advanced Hip Stem within 30 days postoperative will be evaluated and compared with rates reported for other primary hip stems in the literature.

The close relationship between the seating height of the Secur-Fit Advanced Hip Stem and its associated femoral broach will also be demonstrated by intraoperatively measuring the component exposure or countersink upon final seating.

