3.0 Change: *Number Cases*

[name]

Previous language: Cases will be enrolled until 326 cases have received the Secur-Fit Advanced Hip Stem.

New language: Cases will be enrolled until 314 cases have received the Secur-Fit Advanced Hip Stem.

Rationale for Change: Reduction of cases to 314 poses no risk to the statistical analysis and demonstration of long-term safety and effectiveness of the Secur-Fit Advanced Hip Stem.

Change: Primary Objective

Previous language: To evaluate and determine the success rate, defined as absence of stem revision for aseptic loosening or femoral fracture, at 5 years postoperative with the Secur-Fit Advanced Hip Stem.

New language: To evaluate and determine the success rate, defined as absence of stem revision for aseptic loosening or device-related femoral fracture, at 5 years postoperative with the Secur-Fit Advanced Hip Stem.

Rationale for Change: Clarification that femoral fractures which are unrelated to the study device will not be included in primary analysis.

Change: Secondary Objective

Previous language: To evaluate rate of femoral fracture among patients implanted with the Secur-Fit Advanced Hip Stem within 30 days postoperative, and compare with rates reported for other primary hip stems in the literature.

New language: To evaluate rate of device-related femoral fracture among patients implanted with the Secur-Fit Advanced Hip Stem within 30 days postoperative, and compare with rates reported for other primary hip stems in the literature

Version	Description	Changed By
	Rationale for Change: Clarification that femoral fractures	
	which are unrelated to the study device will not be included	
	in the secondary endpoint evaluation.	
	Change: Secondary Objective	
	Previous language: To demonstrate that surgeons can use	
	the Secur-Fit Advanced Hip Stem to consistently match a	
	preoperative plan for femoral head center, offset and leg	
	length postoperatively.	
	New language: [Removal of endpoint]	
	Rationale for Change: This secondary objective is no longer	
	required to support Stryker's business needs, and removal	
	does not affect safety or performance.	

Table of Contents

S	STUDY SYNOPSIS2					
E	VALUA	FION SCHEDULE	8			
1	INT	RODUCTION	9			
	1.1 1.2 1.3 1.4	BACKGROUND STUDY DEVICE PRECLINICAL DATA CLINICAL DATA TO DATE	10			
2	STU	DY OBJECTIVES	12			
	2.1 2.1.1 2.1.2 2.1.3 2.2	Secondary	12 12 12			
3	CLI	NICAL STUDY PLAN	14			

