- To evaluate all-cause revision and removal rates with the Secur-Fit Advanced Hip Stem and compare with those reported for other primary hip stems in the literature.
- To evaluate rate of device-related femoral fracture among patients implanted with the Secur-Fit Advanced Hip Stem within 30 days postoperative, and compare with rates reported for other primary hip stems in the literature.
- To demonstrate the close relationship between the seating height of the Secur-Fit Advanced Hip Stem and its associated femoral broach.

	Function and health related quality of life (QOL) will be compared between the Securifit Advanced Him Stem and published results.			
	between the Secur-Fit Advanced Hip Stem and published results for other primary hip systems, the following outcomes measures will be collected:			
	○ Harris Hip Score (HHS)			
	○ Short Form-12 (SF-12)			
	 Lower Extremity Activity Scale (LEAS) 			
Additional Data	∘ EQ-5D			
Collection	 1-year, 2-year and 5-year SF-12,LEAS and HHS will be presented with respect to improvement from preoperative scores. EQ-5D data will be summarized and presented. An additional Follow-up Questionnaire will be administered annually in postoperative years 3, 4 and 6-10 to assess patient satisfaction and pain, and to capture adverse events. 			
	Radiographic stability and complications will be compared between those implanted with the Secur-Fit Advanced Hip Stem and published results for other primary hip systems.			
Number of Cases	Cases will be enrolled until 314 cases have received the Secur-Fit Advanced Hip Stem.			

Inclusions:

- A. Patient has signed an IRB/EC approved, study specific Informed Patient Consent Form.
- B. Patient is a male or non-pregnant female, skeletally mature and age 21-75 years at time of study device implantation.
- C. Patient has a diagnosis of Non-Inflammatory Degenerative Joint Disease.
- D. Patient is a candidate for primary total hip arthroplasty.
- E. Patient is willing and able to comply with postoperative scheduled clinical and radiographic evaluations and rehabilitation.

Exclusions:

- F. Patient has previously undergone open surgical intervention on the operative hip.
- G. Patient has a prior femoral fracture, with or without deformity, on the operative side.
- H. Patient has an existing total hip replacement on the contralateral side.
- I. Patient requires simultaneous bilateral total hip replacement.
- J. Patient has a Body Mass Index (BMI) > 45.

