8.1 Reporting of Adverse Events

The AE reporting requirements for this study are as follows:

- All AEs that meet the definition of serious and occur within the perioperative period (intraoperative to hospital discharge)
- All AEs related to the operative site, regardless of seriousness or time of occurrence

On postoperative functional evaluations, investigators and SCs will be prompted to question subjects as to whether they have seen a doctor for any reason, been hospitalized for any reason or have a current impediment to their function.

Additionally, SCs will be responsible for following up with the subjects regarding any questionable responses received on the Follow-up Questionnaire administered in postoperative years 6

through 10. If it is determined upon this further investigation that a protocol-defined AE has occurred, the SC will be responsible for completing an AE eCRF, submitting the event to Stryker and reporting to the IRB/EC, as required.

The following decision tree facilitates identification of AEs for which reporting is required under this study protocol:

[figure not shown]

Figure 4. Adverse Event Decision Tree

General Physical Examination Findings

At screening for inclusion into the study, any clinically significant abnormality should be recorded as a preexisting condition and reported on the Demographics eCRF. From the time of consent forward, any new clinically significant findings or abnormalities that meet the definition of a protocol defined AE must also be recorded and documented as an AE.

Adverse Event Reporting Period

The study period during which AEs must be reported is normally defined as the period from the initiation of any study procedures to the end of the study treatment follow-up. The start of study procedures is considered to be the point of consent. Any AEs which fit the protocol defined reportable events must be reported from the time of consent until study completion.

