Intraoperative fissure, fracture, or perforation of the femur, acetabulum or trochanter can occur

due to impaction of the component into the prepared femoral canal or acetabulum. Postoperative

femoral or acetabular fracture can occur due to trauma, the presence of defects or poor bone

stock.

Metal sensitivity reactions have been reported following joint replacement.

AEs may necessitate reoperation, revision, arthrodesis of the involved joint, girdlestone or

amputation of the limb.

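### The 30-day fracture objective counts only device-related fractures of the study stem but sets them against published rates with no matching restriction

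*Combined protocol and SAP*

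**What the plan says.** Section 2.1.2 defines the study side of the comparison: "the rate of device-related femoral fracture among patients implanted with the Secur-Fit Advanced Hip Stem within 30 days postoperative will be evaluated and compared". The other side follows directly, as the figure is to be "compared with rates reported for other primary hip stems in the literature". The Objectives in the Study Synopsis have the same structure, with the filter on the study stem and then the instruction "and compare with rates reported for other primary hip stems in the literature".

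Section 9.1.2 lists the device-related 30-day rate as a secondary efficacy parameter. Section 9.1.4 says it will be evaluated, and the synopsis methodology says it will be reported. None of these places names a published source, a reference value, a fracture definition for the literature side, an interval, a test or a margin.

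Four other places bear on the point:

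- Section 8.1 collects "All AEs related to the operative site, regardless of seriousness or time of occurrence", so fractures not attributed to the device are captured too.
- Section 9.2.2 tabulates all protocol-defined adverse events, without a 30-day cut.
- Section 2.2 plans to compare operative-site events with published data. Section 12.3 lists intraoperative and postoperative femoral fracture among the known complications and says complication rates will be set against published ones.
- Section 12.2 says that postoperative "femoral or acetabular fracture can occur due to trauma, the presence of defects or poor bone" stock. Just before that, it ascribes intraoperative fracture to impaction of the component.

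**The concern.** A literature comparison is informative only if both sides count the same thing. Here one side passes through a causal judgement and the other, as written, does not. Device-related fractures are a subset of all fractures, so against an all-fracture source the filtered figure can only be equal or lower, even if every relatedness judgement is correct.

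The filter could well remove some events. Section 12.2 names causes of postoperative fracture, such as trauma, that an investigator could reasonably judge unrelated to the stem. The plan has no criteria for a device-related fracture. Section 8.3 leaves relatedness to the investigator, and the independent reviewer in Sections 2.1.3 and 3.1 reads radiographs and is not assigned attribution.

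At stake is one of three secondary objectives, for a press-fit stem. An ordinary early fracture rate could be presented as a low one. The neighbouring objective in Section 2.1.2 avoids the problem, because it compares all-cause revision and removal with the literature.

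**Working it through.** **Plan's own figure.** There is none to reproduce for this objective. The sample sizes in Section 9.4.2 concern the 5-year primary endpoint and do not bear on it.

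**Inputs.**

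- From the plan: n = 314 cases (Section 3.3).
- Assumed, because the documents give neither: a true 30-day all-fracture rate R, the same for the study stem and the published stems, and the share f of fractures judged device-related. The main case is R = 2%, with f = 1, 0.75, 0.5 and 0.25.
- Also assumed: an exact (Clopper-Pearson) 95% interval. The plan specifies no interval for this rate.

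**Step 1: apparent rate.** The study stem's expected rate is f × R, a relative understatement of 1 − f. At R = 2% this is 0.75 × 2% = 1.5%, 0.5 × 2% = 1.0% and 0.25 × 2% = 0.5%. Expected counts are 314 × 0.02 = 6.28 fractures in all, of which 4.71, 3.14 or 1.57 are counted.

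**Step 2: when the interval lies wholly below 2%.** With 314 cases the exact 95% upper limit is 1.76% for 1 event and 2.28% for 2 events. The interval excludes 2% from below only if at most 1 event is counted.

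**Step 3: how often that happens with equal stems.** With p = f × R, P(X ≤ 1) = (1 − p)^314 + 314·p·(1 − p)^313.

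| f | p | P(interval wholly below 2%) |
|---|---|---|
| 1 (no filter) | 2.0% | 1.3% |
| 0.75 | 1.5% | 5.0% |
| 0.5 | 1.0% | 18% |
| 0.25 | 0.5% | 53% |

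For p = 1.0%: 0.0426 + 0.1351 = 0.178.

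**Step 4: range over R.** The same calculation, with the cut-off found in the same way:

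- R = 1%: never, at any f, because even 0 events give an upper limit of 1.17%.
- R = 3% (at most 3 events, upper limit 2.77%): 1.5% unfiltered, then 7.6%, 31% and 79% at f = 0.75, 0.5 and 0.25.
- R = 5% (at most 8 events, upper limit 4.96%): 2.3% unfiltered, then 17%, 61% and 98%.

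**Step 5: one possible result.** Suppose 6 fractures occur by day 30 and 2 are judged device-related. Then 6/314 = 1.91% (95% CI 0.70% to 4.11%) and 2/314 = 0.64% (0.08% to 2.28%). Against an assumed published rate of 1.5%, the point estimate moves from above the benchmark to less than half of it, but both intervals include 1.5%. In a single small-count result, the filter may change the headline contrast without changing what the interval supports.

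**The case against.** A reader might infer that the study stem must look better by construction. The documents do not support that. No published source is named, so the plan lacks a stated matching restriction, but it does not show that the published rates are unfiltered. With a source that applies the same filter, or if every early fracture is judged device-related, there is no bias.

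The filter may also remove little. Section 12.2 ties intraoperative fracture to impaction of the component, which may well be judged device-related. Section 8.2 defines an adverse device effect broadly. Exclusions G and M already bar prior femoral fracture on the operative side and inadequate bone stock. These points stand as limits on the size of the bias, which cannot be computed from the documents. They leave its direction against an all-fracture source unchanged.

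A second tempting reading is that unattributed fractures are never set against published data. Sections 2.2 and 12.3 show otherwise: operative-site events, femoral fracture among them, are to be compared with published rates whatever their cause. Section 8.3 asks for date of onset in the initial report of an event, so a 30-day count could be derived. This softens the problem, but no 30-day all-fracture rate is planned, and the objective still names the filtered figure as the one to compare.

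A third is that a formal error rate is inflated. No test, margin or success criterion attaches to this objective, so the percentages above measure how often the contrast would mislead and are not a type I error of the plan.

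**Conclusion.** The point holds in this form: the 30-day objective restricts the study-stem numerator to device-related fractures and places no matching restriction on the literature rates. Against any all-fracture source, the study rate is therefore equal or too low, by the factor f. At an assumed true rate of 2% for both stems, the apparent rate is 1.5%, 1.0% or 0.5% for f = 0.75, 0.5 or 0.25. The chance of an interval wholly below 2% rises from 1.3% to 5%, 18% or 53%.

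This rests on the assumed R and f, on equal true rates, on the chosen interval, and on the published source counting all fractures. Other values of R give anything from no effect on the interval (R = 1%) to a near-certain one (R = 5%, f = 0.25). The consequence is a misleading descriptive contrast in a secondary objective. It should be corrected, but it does not touch the primary conclusion.

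**What to change.** In Sections 2.1.2, 9.1.2 and 9.1.4, and in the matching synopsis text:

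1. Report all femoral fractures of the operated side from surgery to day 30, with an exact 95% confidence interval.
2. Report the device-related subset as a second line, also with an exact 95% interval.
3. Use the all-fracture line for the literature comparison. Use the device-related line only against sources that apply the same restriction.

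The cost is about one table row and a sentence. The events are already collected under Section 8.1, so no new data, visits or cases are needed, and the sponsor keeps its device-specific figure. The downside is that the compared rate may be higher.

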2.1.3 Additional Data Collection

Clinical Outcomes:

Clinical outcomes will be evaluated with the total HHS, including pain, motion and function, preoperatively and at the 6-week, 1, 2 and 5-year visits. Additional HHS data will be obtained at the 7-year and 10-year time points at investigational sites that choose to bring their subjects in for these optional visits.

Patient Outcomes:

Pain, function and health related QOL will be compared between the Secur-Fit Advanced Hip Stem and reports in the literature for other primary femoral stems on the market. The SF-12 is a 12 item patient self-assessment evaluating health and general well-being. The LEAS is a tool that has been developed and validated to evaluate the level of patient activity. The EQ-5D is a standardized instrument for use as a measure of health outcome. These tools will be used to assess patient health-related QOL and will be collected preoperatively and at the 6-week, 1, 2, 3, 4, and 5-year time points.

A Follow-up Questionnaire will be administered annually in postoperative years 3, 4 and 6-10 to assess patient satisfaction and pain, and to capture AEs. This questionnaire, which will also be completed during each interval through 5 years postoperative at which the subject is not seen by the investigator, will provide the information necessary to create an accurate Kaplan-Meier Survival Curve. Patient outcomes data will also be obtained at the 7-year and 10-year time points at investigational sites that choose to bring their subjects back in for these optional visits, in addition to the required Follow-up Questionnaire described.

Radiographic Outcomes:

To assess radiographic stability as compared with other primary femoral stems, radiographs will be taken and collected in the low AP pelvis and Lauenstein lateral views for the preoperative, 6-week, 1, 2 and 5-year intervals. Additional radiographs will be obtained at the 7-year and 10-year time points at investigational sites that choose to bring their subjects back in for these optional visits.

The low AP pelvis view allows for measurement of the position of the hip center, femoral offset and neck angle, and any leg length discrepancy. The Lauenstein lateral view allows for evaluation of the entire hip joint as well as the femoral head, neck and proximal shaft. Suggested radiographic technique for the views required is included in Appendix C.

Radiographs will be evaluated by an independent reviewer throughout the course of the study. Radiographic analysis of the acetabular component will employ three zones (Zone 1 – Zone 3) in the AP view.^{8,9} Radiographic analysis of the femoral component will employ seven zones (Zone 1 - Zone 7) in the AP views and seven zones (Zone 8 – Zone 14) in the lateral view. Numerous parameters will be reviewed by zone, including radiolucency, hypertrophy, condensation and migration. Radiolucency in at least 50% of a zone and measuring at least 1 mm in width is defined as radiolucency present. Cases that present with subsidence of greater than 5 mm, migration of greater than 5° in any direction or at least 2 mm radiolucency in all zones within a single view will be considered radiographic failures.

